3.6 Baseline Characterization

Each analysis sample will be summarized overall and by treatment group for the following characteristics: randomization site; age, sex, race, ethnicity, El Escorial diagnosis, years since ALS symptom onset, delay between symptom onset and ALS diagnosis, site of ALS symptom

onset, use of riluzole at baseline, ALSFRS-R total score, SVC, APB muscle strength by HHD on the dominant hand, TMS parameters, TTNCS parameters, cramping frequency, cramping pain, fasciculation intensity, fasciculation interference with daily living, fasciculation interference with sleep, and RAND-36 physical and mental summary scores. The magnitude of differences between treatment groups will be summarized using Fisher's exact tests for nominal variables and two-sample t-tests for approximately continuous variables. Note that the p-values yielded by these tests do not estimate the probability that the observed differences are due to chance (which is 1 axiomatically).

3.7 Pharmacodynamic and Clinical Analyses

3.7.1 Primary Analysis of the Primary Pharmacodynamic Endpoint

The primary pharmacodynamic analysis will test the effect of mexiletine on RMT in the mITT sample using a shared-baseline mixed model with fixed effects for visit (4 levels: Screening, Baseline, Week 4, and Week 6), treatment group (3 levels: placebo and 300 and 600 mg/day mexiletine) x post-baseline visit (2 levels) and random participant-specific intercepts and slopes with unstructured covariance. The interaction between fixed effects for treatment group and visit will be restricted to post-baseline visits by including a numeric indicator variable (0 pre-treatment, 1 post-treatment) in the interaction. Use of a shared baseline reflects the true state of the population sampled prior to randomization and has the advantage of adjusting for any chance differences at baseline in a manner similar to analysis of covariance (Liang and Zeger, 2000) with potentially greater efficiency with more than one follow-up visit and drop-out. Random participant-specific slopes will be estimated per month from treatment initiation. Data from Final Safety Visits will be assigned to the closed scheduled post-baseline visit. The following SAS code specifies the model:

```
proc mixed data=xxx method=reml;
  class id trtrnd visit;
  model Value = visit post*trtrnd*visit;
  random intercept month / subject=id type=un;
```

The primary estimand will be the comparison of the average change in RMT from pre-treatment to Week 4 for the two active groups vs. placebo, tested using a two-tailed Wald-test at alpha = 0.05. The estimate and its 95% confidence bounds will be obtained by a linear contrast of adjusted means. The following SAS code specifies the linear contrast (with the sort order for treatment group being placebo, 300 mg/day mexiletine, and 600 mg/day mexiletine, and the sort order for visit being chronological):

```
estimate "3|ActvsPlb|dWk 04"
  post*trtrnd*visit 0 0 -2 0  0 0 1 0  0 0 1 0 / cl divisor=2;
```

A significant mean reduction in RMT from pre-treatment to the Week 4 among participants randomized to either 300 or 600 mg/day mexiletine relative to mean changes among participants randomized to placebo would be considered evidence that mexiletine is effective in reducing cortical hyperexcitability.

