13.6. Analysis of Primary Outcome Measure

The effect of mexiletine on RMT will be estimated from a modified intention-to-treat sample (all participants receiving at least one dose of study drug, classified according to randomization) using a shared-baseline repeated-measures two-way ANOVA with fixed effects of visit (4 levels) and treatment x post-baseline visit interaction ($2 \times 2 = 4$ levels) and unstructured covariance among repeated measures (10 terms). Use of a shared baseline reflects the true state of the sample prior to randomization and has the benefit of adjusting for chance baseline differences in RMT across the three treatment groups and improved power similar to ANCOVA. Treatment-dependent differences in the 4-week change in RMT and any sustained benefit at 8 weeks will be estimated using linear contrasts of the least-square means. Not knowing whether a linear dose effect will be present, the primary test will compare each active arm to placebo, using Dunnett's method to control for multiple comparisons. A secondary analysis will test for linear dose response. The proposed mixed effects model makes efficient use of observed data and is unbiased in the presence of loss to follow-up if the probability of loss to follow-up is predictable from observed RMT results. Additional covariates may be included in the primary analysis if rates of loss to follow-up are higher among participants randomized to mexiletine. Wilcoxon rank sum tests of changes from baseline for each active arm vs. placebo and each follow-up time point, imputing the worst observed outcome for missing data, will be evaluated as a sensitivity analysis. The final primary model will be specified prior to unblinding. An additional secondary analysis will look at the effect of mexiletine dosing as achieved, using the estimated serum mexiletine level in place of treatment group. Subgroup differences will be tested by including subgroup, subgroup x visit, and subgroup x treatment x post-baseline visit terms. Subgroups of interest will be pre-specified prior to unblinding.

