This Statistical Analysis Plan (SAP) defines the outcome measures and analysis samples and specifies the planned analyses of data from [name] Mexiletine II trial. This SAP is specific to analysis of data related to the ALS participants in the randomized intervention trial. The SAP supplements the clinical protocol. Please refer to the clinical protocol for details on the rationale for the intervention, eligibility criteria, conduct of the trial, clinical assessments and the timing of their use in the trial, definitions and reporting of adverse events, data management conventions, and regulatory oversight and compliance procedures. In case of discrepancies between the SAP and the clinical protocol concerning matters of analysis, the SAP is authoritative. On all other matters, the clinical protocol is authoritative.

2. Study Design

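### The SAP replaces the protocol's unstructured visit covariance with random intercepts and a single monthly slope, without explanation or safeguard, so the primary standard error rests on an unsupported structure and could err in either direction

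*SAP*

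**What the plan says.** Protocol 13.6 describes a shared-baseline repeated-measures model over four visits with "unstructured covariance among repeated measures (10 terms"). Four visits give 4 x 5 / 2 = 10 variances and covariances, so this is the full visit matrix.

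SAP 3.7.1 keeps the shared baseline and the categorical visit means ("model Value = visit post*trtrnd*visit") but specifies "random participant-specific intercepts and slopes with unstructured covariance". The only covariance statement in the printed code is "random intercept month / subject=id type=un". There, unstructured refers to the 2 x 2 matrix of intercept and slope. With one residual variance, that makes four parameters. On the time scale the SAP says: "Random participant-specific slopes will be estimated per month from treatment initiation".

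The primary contrast, pooled active arms against placebo at Week 4, is "tested using a two-tailed Wald-test at alpha = 0.05". The code names no degrees-of-freedom method and no empirical (sandwich) SE.

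On precedence, the SAP states: "In case of discrepancies between the SAP and the clinical protocol concerning matters of analysis, the SAP is authoritative". Protocol 13.6 also leaves room for a later choice: "The final primary model will be specified prior to unblinding". The change is therefore permitted, but the SAP does not explain it.

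**The concern.** Under the SAP model, the covariance between two visits at times s and t is g00 + (s + t)g01 + st·g11, plus a constant residual variance on the diagonal. This form cannot reproduce correlation that fades with the gap between visits, or a Week 4 visit whose variance stands apart from its neighbours. Week 4 is also the only on-drug visit: Screening and Baseline precede treatment, and Week 8 follows a four-week washout.

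The primary p-value and interval use the model-based SE. If the four-parameter form is wrong, that SE is wrong, and nothing in the plan would reveal it:
- SAP 3.7.2 promises to examine alternative modelling assumptions but lists no alternative covariance.
- SAP 3.7.7 allows sensitivity analyses only for missing data, and only above 20% missing.
- The Wilcoxon sensitivity analysis in Protocol 13.6 is not carried into either SAP section.

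The same model serves the dose and washout contrasts (SAP 3.7.2) and all continuous secondary and exploratory endpoints (SAP 3.7.3).

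**Working it through.** **The plan's own figure.** SAP 3.4 gives 80% power for a 5.3% difference, SD 5.1%, two-sided alpha 0.027, 60 randomized 1:1:1 with 10% loss (18 per arm). The SE for one dose against placebo is 5.1 x √(2/18) = 1.70, and 5.3/1.70 = 3.12. Subtracting the critical value 2.21 gives 0.91, so power is 0.818 by normal approximation. The noncentral t with 51 df gives 0.797. The 80% is reproduced. It comes from a one-way ANOVA, so the covariance change does not affect it.

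**Method.** For each assumed true covariance, take the large-sample limit of the SAP's random-intercept-and-slope fit. Compare its model-based SE for the primary contrast with the true SE of the same estimator, at 18 per arm with complete data. With ratio r = model SE / true SE, the type I error is 2Φ(-1.96r).

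**Inputs.** From the documents: SD of 4-week change 5.1%, 18 evaluable per arm, Screening 0 to 21 days before Baseline. Assumed: between-person SD 12, Screening 0.5 month before Baseline unless stated, and every covariance below. The documents give no visit-specific variance or between-visit correlation.

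**Two cases by hand.** With unstructured covariance, the variance of the contrast is V x (1/36 + 1/18) = V x 0.0833, where V is the Week 4 variance given Screening and Baseline.

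- Compound symmetry: residual variance 5.1²/2 = 13.005 and intercept variance 12² = 144. V = 13.005 x [1 + 144/(288 + 13.005)] = 19.23, so SE = √(19.23 x 0.0833) = 1.266. The SAP model also gives 1.266, so the richer model costs no large-sample precision here.
- Intercept plus exponential decay (serial correlation 0.5 per month, both variances 5.1² = 26.01): V = 26.01 x 0.865 = 22.50, so SE = 1.369. The SAP model reports 1.255, while its true SE is 1.379. The ratio is 0.91 and the type I error is 2Φ(-1.784) = 7.4%. The reported 95% half-width is 1.96 x 1.255 = 2.46, when it should be 1.96 x 1.379 = 2.70.

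**Range of cases (large-sample).**

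| Assumed covariance | SAP ratio r | Type I error | Unstructured ratio |
|---|---|---|---|
| Compound symmetry | 1.00 | 5.0% | 1.00 |
| True random intercept and slope | 1.00 | 5.0% | 1.00 |
| Intercept plus decay; Screening at -0.25 / -0.5 / -0.7 month | 0.86 / 0.92 / 0.95 | 9.0 / 7.3 / 6.3% | 1.00 |
| Random walk plus noise | 0.94-0.98 | 6.5-5.5% | 1.00 |
| Extra Week 4 variation, all arms, SD 2 / 3 / 4 | 0.94 / 0.89 / 0.84 | 6.4 / 8.0 / 9.8% | 1.00 |
| Extra Week 4 variation, active arms only, SD 1 to 5 | 0.998 to 0.957 | 5.1-6.1% | 1.01-1.14 |
| Week 8 residual variance x 1.5 | 1.06 | 3.8% | 1.00 |
| Week 4 residual variance x 0.7 | 1.075 | 3.5% | 1.00 |

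**Finite-sample check.** REML fits to 600 simulated null trials of 54 complete participants (Wald z, Monte Carlo error about 0.9 points) gave these rejection rates for the SAP model: 4.2% (compound symmetry), 4.0% (random slopes), 6.7% (intercept plus decay), 4.7% (exponential correlation plus noise) and 4.8% (active-arm drug response, SD 3). The unstructured model gave 3.7-4.7%.

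**The case against.** A reader might infer that the SAP's SE is too small in most plausible cases and that the test therefore exceeds 5%. The documents do not support that, because the direction depends on a covariance they never give. Two sweeps of 300 arbitrary structures disagree. Mixing intercept, serial, slope and noise components, 69% of ratios fell below 0.995 and 21% above 1.005, with median 0.98. With unequal visit noise and no serial correlation, 45% were too small and 50% too large. In the finite-sample check only one of five cases exceeded 5%, by about two Monte Carlo errors.

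A second tempting inference is that one line through the on-drug and washout visits contradicts the design. The line applies only to between-person covariance; the mean pattern over visits is unrestricted in each arm. Only the active arms go on and off drug, and extra Week 4 variation confined to them costs the SAP's SE at most about 4-5%. The larger shortfalls need serial correlation or a noisier Week 4 in placebo as well, for which the documents give no specific reason.

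Four parameters can also be defended with about 60 participants and further losses to RMT quality flags. A slope in months uses actual timing, including a Screening gap of up to 21 days, which a visit-indexed matrix ignores. The SAP may also legitimately depart from the protocol.

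All of this limits the claim. It does not supply the missing rationale or a check on the covariance. The unstructured SE was correct in every common-covariance case tried, including those where the SAP model fails.

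**Conclusion.** The point stands in limited form. SAP 3.7.1 adopts a more restrictive covariance than Protocol 13.6, gives no reason, and includes nothing to protect the primary inference if it is wrong. Under the assumed covariances, the SE ranges from about 15% too small to about 8% too large and is exact under two ordinary structures. Type I error at a nominal 5% runs from about 3.5% to just under 10% in large samples.

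These sizes rest on the assumed covariances and Screening gaps, complete data and 18 per arm. With complete data the treatment estimate is unbiased. With missed visits, the missing-at-random argument in SAP 3.7.7 also relies on the covariance being right; that effect was not quantified. The change is worth making because it is cheap and returns to the trial's own protocol model, not because the SAP test has been shown to be invalid.

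**What to change.** Before unblinding, replace the random statement with `repeated visit / subject=id type=un;` and add `ddfm=kr` as an option on the existing model statement. The Kenward-Roger choice is new: Protocol 13.6 names no degrees-of-freedom method, so the SAP should present it as an addition. Keep the random-slope model as the named fallback if the unstructured fit does not converge, and otherwise as a sensitivity analysis.

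If the sponsor prefers the random-slope model as primary, the SAP should give the reason and add an unstructured-covariance or robust-SE sensitivity analysis.

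The cost is two short code edits and six more covariance parameters (10 - 4). If only the active arms become more variable at Week 4, the pooled unstructured matrix overstates the SE, by 1-14% for an extra SD of 1 to 5. The repeated statement also needs one record per participant per visit. Because Final Safety Visit data are assigned to a scheduled visit, the SAP needs a rule for choosing between two records that fall on the same visit.

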5.4 Randomization Procedures

A permuted-block randomization schedule, stratified by site and use of riluzole at screening, will be developed by the study statistician with assignments in a 1:1:1 ratio among 300 mg/day oral mexiletine, 600 mg/day oral mexiletine, and placebo. If a randomized subject withdraws from the study prior to initiating study drug, their assignment will be released and re-used.

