6.3. Method of Assigning Study Subjects to Treatment Groups (Randomization)

Each subject who meets all eligibility criteria, is accepted for the study, and signs an informed consent form will be randomized to receive mexiletine 300 mg/day or mexiletine 600 mg/day or placebo on a 1:1:1 basis. Randomization will be stratified by site and use of riluzole at screening.

The randomization scheme will be independently developed by the Biostatistics Center and will indicate the treatment assignment and the subject numbers to be used by each site. A programmer in the Biostatistics Center will develop the plan under the guidance of the chief biostatistician.

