2.4 Participant Flow

After a site is activated for recruitment of ALS participants and after each ALS patient provides informed consent and is determined eligible, approximately 60 participants will be randomized to receive placebo, 300 mg/day oral mexiletine, or 600 mg/day oral mexiletine in a 1:1:1 ratio, stratified by clinical site and use of riluzole at screening. Participants are first dose of study drug is administered at the baseline visit and are intended to remain on study drug for 4 weeks. After baseline, participants receive a telephone call at week 1 and complete in-clinic evaluations at weeks 4 and 8. Participants who discontinue study drug should remain on study following the normal schedule of assessments. Patients withdrawing consent are asked to delay withdrawing consent until after they return for a Final Safety Visit within 2 weeks after their last dose of study drug and after they complete a final telephone call 4 weeks after their last dose of study drug.

Detailed descriptions of study procedures and timing are specified in the clinical protocol.

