2.5 Treatment Allocation

Prior to the baseline visit, eligible participants are randomly allocated in equal proportions to one of three treatment groups (placebo, 300 mg/day oral mexiletine, or 600 mg/day oral mexiletine) according to a permuted-block randomization schedule, stratified by site and use of riluzole at screening. The randomization schedule was prepared by computer program by the unblinded study statistician.

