3.7.4 Subgroup Analyses

Differences in treatment efficacy will be explored in several pre-defined subgroups: baseline RMT (median split) and baseline riluzole use (yes vs. no). Subgroup specific estimates will be obtained by including subgroup, subgroup \times visit, and subgroup \times treatment \times post-baseline visit terms to models for primary and secondary pharmacodynamic outcomes using the mITT sample.

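### Randomisation is stratified by site and riluzole use at screening, but the primary RMT model includes neither; the test stays valid, and adding riluzole terms is a cheap, small improvement

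*SAP*

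**What the plan says.** SAP 2.5 describes a "permuted-block randomization schedule, stratified by site and use of riluzole at screening", and SAP 2.4 repeats the two factors. Protocol 5.4 and 6.3 agree; the latter reads "Randomization will be stratified by site and use of riluzole at screening".

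The primary analysis in SAP 3.7.1 uses fixed effects for visit and for treatment by post-baseline visit, plus random participant intercepts and slopes. The code line is "model Value = visit post*trtrnd*visit". Protocol 13.6 has a different covariance structure but also no site or riluzole term.

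Elsewhere in the SAP, site is only tabulated (3.6). Riluzole enters a model only in the exploratory subgroup analysis (3.7.4), where it is defined by use at baseline rather than at screening. Section 3.7.3 reuses the primary model for the continuous secondary and exploratory endpoints.

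Protocol 13.6 has one covariate provision: "Additional covariates may be included in the primary analysis if rates of loss to follow-up are higher among participants randomized to mexiletine". The SAP does not repeat it, and the SAP introduction states "In case of discrepancies between the SAP and the clinical protocol concerning matters of analysis, the SAP is authoritative".

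**The concern.** Factors used to restrict the randomisation are normally carried into the primary model. If they predict the outcome, stratified allocation reduces the true variability of the treatment estimate, but a model without them does not credit that reduction. The reported standard error is then too large and the test is conservative.

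The shared baseline and the participant intercepts absorb differences between strata in the level of RMT. They do not absorb differences in the 4-week change, which is the endpoint. The term that matters is therefore riluzole by visit; a riluzole main effect alone would add little.

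At stake are a little precision and clarity of pre-specification. Without a stated plan, any stratum-adjusted result reported later would be post hoc.

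**Working it through.** **Inputs from the documents.** SD of 4-week RMT change 5.1; 60 randomised 1:1:1; up to 10% loss, so 18 evaluable per arm; target effect 5.3; two-sided alpha 0.027 per dose (SAP 3.4). The primary contrast is pooled active against placebo at two-sided 0.05 (SAP 3.7.1). About 9 sites (SAP 2.3), so 9 x 2 = 18 strata and 60/18 = 3.3 participants per stratum.

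**The plan's own figure.** For one dose against placebo, SE = 5.1 x sqrt(2/18) = 1.70 and 5.3/1.70 = 3.12. A noncentral t with 51 degrees of freedom gives 79.7% power, and 80% power at 5.32. Dunnett's per-comparison alpha comes to 0.0271. The stated 80% at 5.3 is reproduced, and it does not rely on adjustment for strata.

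For the pooled contrast, SE = 5.1 x sqrt(1/36 + 1/18) = 1.47. Its own 80% effect is 4.20 at alpha 0.05, so 4.2 is used below.

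**Simulation of the SAP mixed model.** 6000 trials per cell, REML, Kenward-Roger degrees of freedom. Assumptions not in the documents: 60% riluzole use, intercept SD 12, residual SD 3, visits at months -0.5, 0, 1 and 2, blocks of 3, and a stratum effect of equal size at both post-baseline visits. The strata's share of the variance in change is assumed to be 0, 5, 10 or 20%, half from riluzole and half from site.

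Model A is the SAP model. B adds riluzole and riluzole by visit. C adds a random site by visit effect to B.

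| Share | Reported SE, B/A | True SD, B/A | Power A | Power B | Power C | Type I error A | Type I error B | Reported SE, C/A |
|---|---|---|---|---|---|---|---|---|
| 0% | 1.003 | 1.003 | 82.3% | 82.1% | 82.3% | 0.056 | 0.056 | 0.998 |
| 5% | 0.997 | 0.999 | 83.7% | 83.8% | 84.0% | 0.050 | 0.050 | 0.991 |
| 10% | 0.991 | 0.995 | 86.2% | 86.8% | 87.0% | 0.049 | 0.045 | 0.983 |
| 20% | 0.975 | 0.984 | 90.2% | 91.0% | 91.6% | 0.046 | 0.048 | 0.958 |

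The Monte Carlo error of the type I rates is 0.003. The true SD falls less than the reported SE, which shows that stratified allocation has already secured most of the real precision. Over all settings run (also blocks of 6, residual SD 2, and 80% riluzole use), B changes power by -0.3 to +1.5 points. In C the site variance was estimated as zero in 54, 50, 44 and 32% of trials.

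**If the stratum effect grows linearly with time.** Runs of 1000 trials, residual SD 2.8, effect 4.2:
- Riluzole share 5%: mean SE 1.453 to 1.407 (ratio 0.968), power 79.8% to 80.8%.
- Riluzole 10% plus site 10%: mean SE 1.453 to 1.360 (ratio 0.936), true SD 1.323 to 1.300 (ratio 0.983), power 84.5% to 87.1%. Type I error is 0.029 without and 0.034 with the riluzole terms (Monte Carlo error about 0.007), so the test is conservative.

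Further runs of this kind gave gains of 2.4 to 3.1 points.

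**How plausible is a 20% share?** With riluzole explaining half of it and 60% of participants using it, users and non-users must differ in 4-week change by sqrt(0.10 x 5.1² / (0.6 x 0.4)) = sqrt(2.601/0.24) = 3.29 points. That is 3.29/5.3 = 62% of the target effect. Even then, typical chance imbalance in riluzole use (SD 6.5 to 9.0 percentage points) shifts the estimate by only 3.29 x 0.065 = 0.21 to 3.29 x 0.090 = 0.30 points, against a standard error of about 1.4.

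**The case against.** The strongest reply is that nothing is broken. The test is valid, the power statement holds, and at shares of 0 to 5%, the credible end, the riluzole terms gain nothing or lose a fraction of a point. That stands, and it is why the point is minor.

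Other replies stand in part:
- **Effect size.** 4.2 is not in the documents; it is the pooled contrast's own 80% effect. At the stated 5.3, power with the simulated standard errors is already about 96 to 98%, and the terms change it by -0.1 to +0.4 points.
- **Degrees of freedom.** The SAP code has no Kenward-Roger option. Runs without it, with the equal-size stratum effect, gave type I error of 0.042 to 0.058 for the planned model, so the conclusion on validity does not change.
- **Site.** A site by visit variance is hard to estimate here, and C's slightly smaller SE at a zero share cannot be real precision. This supports keeping site out of the primary model.
- **Existing riluzole model.** SAP 3.7.4 already fits riluzole and riluzole by visit, but together with a treatment interaction and as an exploration. It does not yield a stratum-adjusted primary estimate.
- **The protocol's covariate option.** It may survive, since the SAP supplements the protocol, but its trigger is differential loss to follow-up, not stratification.
- **Central reading.** It is a weak safeguard against site effects on RMT, because the value is entered by hand at the site (Protocol 7.2.1) and the central reader grades its quality.

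**Conclusion.** The concern holds and is minor. Neither document carries the stratification factors into the primary model or says why. The planned test remains valid and is at worst conservative; no sample-size figure changes.

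Adding the riluzole terms changes the reported standard error by between +0.3% and -2.5% in the main runs (blocks of 3), and by about -6% if a strong stratum effect accumulates over time. Power moves by -0.3 to +1.5 points, or up to about +3 in the accumulating case.

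These sizes rest on the assumed share of variance, riluzole prevalence, block size and variance components, none of which the documents give. Small stratum effects are more credible: riluzole dosing is to stay stable (Protocol 5.2), the same physiologist should test each participant, and each physiologist must first pass a three-day reproducibility check (Protocol 7.2.1). The main benefit is an analysis that matches the randomisation and is fixed before unblinding.

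**What to change.** - **SAP 3.7.1:** add riluzole use at screening, taking the value used for stratification, and riluzole by visit as fixed effects. In the code, append the variable (say `rilscr`) to the end of the class statement and add `rilscr rilscr*visit` to the model statement. Placing it last leaves the coefficient order, and so every estimate statement, unchanged.
- **SAP 3.7.2 and 3.7.3:** carry the terms into the secondary contrasts and the continuous endpoints.
- **SAP 3.7.2:** pre-specify two sensitivity analyses: the current model without strata, and a model that also adjusts for site, for example by a random site by visit effect with Kenward-Roger degrees of freedom. State that site is left out of the primary model because there are only about 3.3 participants per stratum. Fixed site terms are not a better choice: in an ANCOVA approximation with no stratum effect, adding riluzole and eight site terms took power from 85.7% to 83.1%.

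If the sponsor prefers the present model, one sentence giving the reason would be enough.

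**Cost:** SAP wording, two edited lines in the primary code, two short sensitivity models and no new data. The terms use 1 + 3 = 4 degrees of freedom. If riluzole does not predict change, the standard error is 0.3 to 0.5% larger and power 0.2 to 0.3 points lower.
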